Quantitative observational comparative effectiveness of quadratus lumborum block with liposomal bupivacaine (Exparel®) versus thoracic epidural analgesia in patients undergoing laparoscopic colectomy

NCT03827291

Document Date: 09/27/2022

Purpose of the Study

We believe that a quadratus lumborum block with liposomal bupivacaine(Exparel®) or a quadratus lumborum block with an admixture of bupivacaine will provide roughly equivalent analgesia and opioid use when compared with postoperative analgesia in a historical cohort that received thoracic epidural analgesia. We believe participants who receive the quadratus lumborum block will result in improved early mobilization, fewer complications such as block failure, urinary retention, and pruritis, and decreased overall pharmacy costs compared to the patients who received thoracic epidural analgesia.

Background & Significance

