Block success and adverse events. Presence of demonstrable sensory block over 4 points on the abdomen (one in each of the 4 quadrants), as tested by response to pinprick. Subjects will be asked to report whether the stimulus feels “sharp” or “dull”, indicating block failure and success respectively. This will be done at the time of pain assessment (30 minutes after arrival to PACU, and at time points 8 hrs., 24 hrs., 36 hrs. and 48 hrs. and 72 hrs.). Subjects will be evaluated for potential adverse events related to the block including evidence of hematoma, infection, unexpected sensory or motor deficit, local anesthetic systemic toxicity, as well as transient weakness of the hip flexor muscles (a known possible side-effect of QL block).

Satisfaction with postoperative pain control. Overall subject satisfaction with pain control will be recorded on postoperative day 0 and 1 (11-point scale: 10=highly satisfied, 0=completely unsatisfied)

Hospital length of stay. Measured both by raw length of stay and by time to achieving “discharge readiness”, defined by the presence of 3 criteria: a pain score of 3 or less with ambulation, no opioids required in the preceding 6 hours, and the ability to perform self-care (go to the toilet, dress, and shower).

Incidence of opioid-related adverse events. Incidence of nausea, vomiting, ileus, constipation, orthostasis, pruritis, urinary retention, respiratory depression

Time to first mobilization. Measured from time of arrival in PACU (time zero)

Cost. Hospital costs including pharmacy-related costs, costs due to opioid-related adverse events, the cost associated with nursing interventions and drugs to treat opioid-related adverse events, and overall hospital admission costs will be calculated.

Sleep Quality. Two measures will be taken for sleep quality assessment. How much did pain interfere with falling asleep (0= no interference, 10= completely interferes). How much did pain interfere with staying asleep (0= no interference, 10= completely interferes). Measures will be taken once daily from POD 1 to POD 7 (approximately 168hrs. after surgery). If the subject is sleeping at the time assessment collection is due, the subject will not be disturbed to collect the assessments, and this will not be considered a protocol deviation.

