Historical data of 30 patients that meet inclusion criteria and meet no exclusion criteria, will be collected and for the retrospective group. The anesthesia statisticians will evaluate the following data from the patient's electronic medical record if available, including but not limited to hospital notes, anesthesia notes, medical history, medications, pain service notes, and flowsheets from admission to discharge. Electronic medical records will be used to assess the following items to compare to the prospective cohort.

Opioid consumption. Cumulative opioid consumption at 24hours, 48 hours and 72 hours. 48 hours is the primary outcome measure. Data will be drawn from PACU records and from the nursing medication records.

NRS-11. The 11-point Numeric Rating Scale (0-10) will be used as a secondary outcome measure. These will be collected from the preoperative assessment record, 30 minutes after arrival to PACU, and at time points 8 hrs., 24 hrs., 36 hrs. 48 hrs. and 72 hrs.

Thoracic epidural success and adverse events. Evidence of epidural block success/failure (as described in the anesthesia record and in daily Inpatient Pain Service notes). This will be done at the time of pain assessment (30 minutes after arrival to PACU, and at time points 8 hr, 24 hr, 36 hr and, 48 hr and 72 hr). Subject data will be collected for potential adverse events related to the epidural including evidence of hypotension, urinary retention, inability to ambulate per physical therapy. (known possible side-effect of thoracic epidural approach).

Hospital length of stay. Measured both by raw length of stay and by time to achieving "discharge readiness", defined by the presence of 3 criteria: a pain score of 3 or less with ambulation, no opioids required in the preceding 6 hours, and the ability to perform self-care (go to the toilet, dress, and shower).

Incidence of opioid-related adverse events. Incidence of nausea, vomiting, ileus, constipation, orthostasis, pruritis, urinary retention, respiratory depression

Time to first mobilization. Measured from time of arrival in PACU (time zero)

Cost. Hospital costs including pharmacy-related costs, costs due to opioid-related adverse events, the cost associated with nursing interventions and drugs to treat opioid-related adverse events, and overall hospital admission costs will be calculated.

Selection of Subjects

Criteria for inclusion in Prospective cohort:

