- Patients scheduled for elective, laparoscopic colonic resection by one of three surgeons: Drs. [name], [name] or [name]. These surgeons perform this procedure in the same manner
- Age 18-85 years
- American Society of Anesthesiologists (ASA) Physical Class I-III
- BMI 18-35 kg/m²

Criteria for exclusion in Prospective Cohort:

- Inability to consent
- Inability to speak English
- Pregnancy
- Emergency surgery
- Contraindications to regional blockade: coagulopathy or bleeding diathesis, local infection, allergy to local anesthetics
- Allergies/intolerances/contraindications to any of the multimodal agents (acetaminophen, gabapentin, ketorolac)
- Daily opioid equivalent use of 30 mg of morphine or greater at time of consent
- History of drug or alcohol abuse
- Uncontrolled anxiety, schizophrenia or other psychiatric disorder that, in the opinion of the investigator, may interfere with the study assessments of compliance.

Criteria for inclusion in Retrospective cohort:

- Patients that have had a laparoscopic colonic resection in the past year by Drs. [name], [name] or [name] and received thoracic epidural analgesia.
- Thoracic epidural analgesia must be placed in preoperatively, must be sited between levels T8 and T12, and must be started while the case is going- i.e. not started in PACU.
- Age 18- 85 at the time of the procedure.
- American Society fo Anesthesiologists (ASA) Physical class between I- III.
- BMI 18- 35 kg/m².

- Received the standard multimodal medication regimen for pain as outlined in the ERAS protocol for colorectal surgery

Criteria for exclusion in Retrospective cohort:

- Emergency surgery
- Daily opioid equivalent use of 30 mg of morphine or greater at time of consent.
- History of drug or alcohol abuse.
- Uncontrolled anxiety, schizophrenia or other psychiatric disorder.

Risk/Benefit Assessment

Risks of the study intervention relate to those associated with the quadratus lumborum block. These include routine risks of block procedures including bleeding, infection, nerve damage, local anesthetic systemic toxicity, as well as transient weakness of the hip flexor muscles (a known possible side-effect of QL block).

If subjects receive the quadratus lumborum block, they may experience improved pain control and/or reduced side effects compared to the epidural pain relief option, but it is not known yet whether this will be the case.

Data Analysis & Statistical Considerations

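### Hematoma, infection, unexpected sensory deficit and local anesthetic toxicity are named for evaluation in the QLB cohort but not in the TEA chart abstraction, so these four safety rows have no specified comparator

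*Combined protocol and SAP*

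**What the plan says.** For the prospective cohort, the Assessments item on block success and adverse events has patients evaluated for "evidence of hematoma, infection, unexpected sensory or motor deficit, local anesthetic systemic toxicity", and also for transient hip flexor weakness, which the plan describes as a known possible effect of the QL block.

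For the historical cohort, the item on thoracic epidural success and adverse events has data collected on "potential adverse events related to the epidural including evidence of hypotension, urinary retention, inability to ambulate per physical therapy". The source is the "electronic medical record if available, including but not limited to hospital notes, anesthesia notes", together with pain service notes and flowsheets, from admission to discharge. The introduction to that section says its items are assessed for comparison with the prospective cohort.

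The Risk/Benefit Assessment lists "routine risks of block procedures including bleeding, infection, nerve damage, local anesthetic systemic toxicity" among the hazards of the QLB, and mentions hip flexor weakness separately as particular to the QL block. The Purpose of the Study expects "fewer complications such as block failure, urinary retention, and pruritis" with QLB. Data Analysis & Statistical Considerations plans Fisher exact or Wilcoxon tests for the secondary outcomes and defines no composite of complications.

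**The concern.** The plan's own text makes the four events relevant to both cohorts. It describes bleeding, infection, nerve damage and systemic toxicity as routine to block procedures in general. It speaks of epidural block success and failure, and the Background describes TEA as a local anesthetic infusion usually kept for two days. No reason is given for leaving the four events out of the TEA abstraction.

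A chart abstractor usually records what the form asks for. If an event is not on the form, a blank can later be read as zero. A hematoma or a toxicity episode in the QLB cohort would then stand beside an empty or falsely clean TEA cell. What is at stake is the reading of the safety table. The primary outcome and the sample size are not affected.

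**Working it through.** **No plan figure applies.** The plan states no complication rate and no calculation for complications. Its only computed figure, 27 per group (54 in total) for opioid consumption, does reproduce: 2 × (1.960 + 0.842)² × 5.2² / 4² = 26.5, rounded up to 27, with a margin of 20% of 20 mg = 4 mg and one-sided alpha 0.025. It does not bear on this point except as one possible cohort size.

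**Step 1: the two lists side by side** (Assessments against the historical-data section).

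| Event | QLB | TEA |
|---|---|---|
| Hematoma | named | not named |
| Infection | named | not named |
| Unexpected sensory deficit | named | not named |
| Local anesthetic systemic toxicity | named | not named |
| Motor deficit | named | partial counterpart: inability to ambulate |
| Hip flexor weakness | named (specific to QL block) | not named |
| Hypotension | not named (orthostasis is) | named (orthostasis also) |
| Inability to ambulate | not named (time to first mobilization is) | named (time to first mobilization also) |
| Block failure | "as tested by response to pinprick" | "as described in the anesthesia record and in daily Inpatient Pain Service notes" |
| Urinary retention, pruritus | named | named |

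The last row holds because the opioid-related list, "Incidence of nausea, vomiting, ileus, constipation, orthostasis, pruritis, urinary retention, respiratory depression", is the same in both cohorts.

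**Step 2: chance that the asymmetry shows at all.** P(at least one event) = 1 − (1 − p)^n, where p is an assumed common rate for the four events together. The historical cohort is 30. The Sample Size Justification plans to recruit 45 but does not say whether that is the QLB cohort or a total, so 27 is shown as well.

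| Assumed p | n = 45 | n = 27 | n = 30 (TEA) |
|---|---|---|---|
| 0.1% | 4.4% | 2.7% | 3.0% |
| 2% | 60% | 42% | 45% |
| 5% | 90% | 75% | 79% |

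For example, at 2%: 1 − 0.98^45 = 0.60, 1 − 0.98^27 = 0.42 and 1 − 0.98^30 = 0.45. Expected counts at 2% are 45 × 0.02 = 0.9 and 30 × 0.02 = 0.6.

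**Step 3: what the counts could support.** With 45 against 30, Fisher's exact test needs 7 against 0 to reach p < 0.05 to the disadvantage of QLB (7 vs 0 gives 0.037; 6 vs 0 gives 0.075). With 27 against 27 it needs 6 against 0 (0.023; 5 vs 0 gives 0.051). Expected counts near one are far from this. Even a fully ascertained 0 of 30 excludes only rates above 1 − 0.05^(1/30) = 9.5% (one-sided 95%).

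**Step 4: net direction over all complications.** Suppose every event were equally frequent in both cohorts and each cohort counted only its own list. The spurious QLB minus TEA difference would then be q − h, where q is the rate of items named only for QLB and h the rate of items named only for TEA. With q assumed between 1% and 10% and h between 0% and 30%, it runs from 10 − 0 = +10 points (against QLB) to 1 − 30 = −29 points (against TEA).

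**The case against.** A reader might infer that procedure complications can be counted in one cohort only, and that the fewer-complications comparison is therefore tilted against QLB. The documents do not support that, for four reasons.

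- TEA has its own list of procedure-related events. Both lists are introduced as examples, and the record sources are left open. TEA capture of the four events is unspecified, not ruled out.
- Hypotension and inability to ambulate are named only for TEA. The Background singles out hypotension as the chief drawback of TEA and says it often ends the infusion. That asymmetry runs against TEA, so the net sign is unknown.
- The complications named in the Purpose are collected in both cohorts, although block failure is measured differently. The examples there leave room for other events, but no composite is defined.
- Nothing in the documents ranks the four events as the most serious.

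It can also be argued that the four items are safety monitoring of the study intervention, since the Risk/Benefit Assessment presents them as its risks. Reported that way, they would describe QLB alone and enter no contrast.

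These arguments limit the point but do not remove it. Opposite asymmetries in different events do not cancel in a table read row by row, so adding hypotension for QLB would not repair these rows. The plan does not say that the four items are to be reported for QLB only.

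One further objection stands in part: adding fields to the TEA form leaves bedside examination in one cohort and chart review in the other. The fix therefore has to use the chart as the common source.

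**Conclusion.** The point holds as a minor one, confined to hematoma, infection, unexpected sensory deficit and local anesthetic systemic toxicity. For these rows a QLB event has no specified comparator and a TEA event may be missed, which on these rows alone disadvantages QLB. No overall direction can be claimed.

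The size depends on rates that the plan does not give. If the four events together occur at 2%, an event somewhere is quite likely (60% in 45 or 42% in 27 QLB patients; 45% in 30 TEA patients). At 0.1% it is unlikely (about 4% in 45, 3% in 27 and 3% in 30). These figures assume the same true rate in both cohorts, and the figures for 45 take that number as the QLB cohort, which the plan does not say.

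**What to change.** Add the four events to the TEA abstraction form, from block placement to discharge, with written definitions and an explicit entry for absent as distinct from not documented. Abstract the same four events from the chart, over the same in-hospital window, for the QLB patients. Report the chart-based counts for both cohorts with exact 95% intervals and no test. Show QLB events detected only at the bedside on a separate line.

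The cost is four fields in 30 charts that are already being read, plus the same four fields in the QLB charts: 4 × (30 + 45) = 300 entries if QLB is 45, or 4 × (30 + 27) = 228 if it is 27. Treatment, visits and sample size do not change. The downside is that chart review is less sensitive than bedside evaluation and may undercount in both cohorts. A note beside the table should say so.

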We will use descriptive statistics (mean (SD) or frequency (%)) and group comparisons via Wilcoxon rank sum or fisher exact tests to measure differences between cohorts in opioid consumption, pain scores with rest and activity, and other secondary outcome measures.

Sample Size Justification

A difference in opioid consumption less than 20% would be considered non-inferior. Based on typical postoperative opioid consumption following laparoscopic colectomy (20mg +/- 5.2 mg), a total of 54 subjects (27 in each group) would be required to reject the null hypothesis that QL blockade is inferior in the first 48 hours with the study intervention, given an alpha of 0.05 and a power of 0.8. We plan on recruiting 45 subjects to account for dropout.

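### The plan expects lower overall pharmacy cost with quadratus lumborum block (QLB), but gives no test or interval for the difference in mean cost, only (by inference) a rank-sum test

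*Combined protocol and SAP*

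**What the plan says.** Purpose of the Study states a directional cost hypothesis: "decreased overall pharmacy costs compared to the patients who received thoracic epidural analgesia". The Cost item under Assessments lists pharmacy costs, costs of opioid-related adverse events and their treatment, and admission costs, ending "overall hospital admission costs will be calculated". The same item is listed for the historical cohort, introduced by "Electronic medical records will be used to assess the following items to compare to the prospective cohort".

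Data Analysis & Statistical Considerations is one sentence. It provides "descriptive statistics (mean (SD) or frequency" (as a percentage) for description and "group comparisons via Wilcoxon rank sum or fisher exact tests to measure differences between cohorts". It names opioid consumption and pain scores, then adds "and other secondary outcome measures". Cost is not named there, and no other method is given for a continuous outcome.

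The comparator is historical: "Patients that have had a laparoscopic colonic resection in the past year", with TEA. The documents give no cost distribution, price year, source of unit costs, or power for cost.

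**The concern.** Whether a pathway lowers overall spending depends on mean cost, because the mean times the number of patients is the amount spent. The rank-sum test asks a different question: whether a randomly chosen QLB patient tends to cost more or less than a randomly chosen TEA patient. The two questions agree when the distributions differ only in location. They can disagree when the shapes differ.

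The protocol gives a reason to expect different shapes for pharmacy cost. Design & Procedures gives every QLB patient the same quantity of block drug on each side, so part of the cost is the same for everyone. Background & Significance describes epidurals that typically run for two days but are often discontinued for hypotension, or are patchy or non-functioning, and these costs can be expected to vary more. At equal mean cost, the more skewed cohort has the lower median, and the rank test can report the other cohort as costlier. The stake is the cost conclusion, which is one of the stated expectations of the study.

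**Working it through.** **The plan's own figure.** There is none for cost. The stated 27 per group is for opioid consumption and reproduces with a margin of 20% × 20 mg = 4 mg, SD 5.2 mg, two-sided alpha 0.05 and power 0.80: n = 2(1.960 + 0.842)² × 5.2² / 4² ≈ 26.5, rounded up to 27. It is used below only as a possible group size.

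**Inputs.** From the documents: 30 TEA patients. Assumed: 45 QLB patients (Sample Size Justification says 45 will be recruited but gives no split by group), with 27 as an alternative; lognormal costs; equal true means; and the log-scale SDs in the table.

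**Why the rank test moves when the means do not.** For a lognormal cost with mean m and log-SD s, the log-scale mean is ln m − s²/2. With equal m in both cohorts:

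- ratio of medians, QLB/TEA = exp[(s_T² − s_Q²)/2]
- P(QLB cost > TEA cost) = Φ[(s_T² − s_Q²) / (2√(s_T² + s_Q²))]

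Example, s_Q = 0.4 and s_T = 0.6: (0.36 − 0.16)/2 = 0.10, so the median ratio is exp(0.10) = 1.105. Also 0.10/√0.52 = 0.139, so P = 0.555. A probability of 0.5 would mean that the rank test has nothing to detect.

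**Simulated two-sided 0.05 Wilcoxon test, 45 QLB and 30 TEA, equal means.** The last column is the share of trials that are significant with QLB higher; 2.5% is expected.

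| Log-SD QLB / TEA | Median ratio | P(QLB > TEA) | QLB declared costlier |
|---|---|---|---|
| equal | 1.000 | 0.500 | about 2.5% |
| 0.4 / 0.5 | 1.046 | 0.528 | about 7% |
| 0.4 / 0.6 | 1.105 | 0.555 | about 14% |
| 0.2 / 0.6 | 1.174 | 0.600 | about 35% |
| 0.3 / 0.8 | 1.317 | 0.626 | about 44% |
| 0.3 / 1.0 | 1.576 | 0.669 | about 67% |

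Repeat runs of the last three rows gave 33–35%, 44–46% and 67–69%. With 27 QLB patients they span 26–59%. In these three rows QLB was declared cheaper in under 0.3% of trials, and a Welch t test of the means rejected, in either direction, in about 7%, 8% and 11%.

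**The fixed drug cost modelled directly.** Give QLB a fixed cost plus a lognormal remainder with the same log-SD as TEA (0.4 or 0.6), equal means, 45/30. QLB is declared costlier in about 3% of trials when the fixed part is 3% of mean cost, 3–5% when it is 10%, 5–8% when it is 20%, and 14–24% when it is 50%.

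**Price drift, as a separate check.** With 30 TEA and 45 QLB, log-SD 0.2 in both cohorts and no difference in resource use, an assumed price rise of 3% or 5% between cohorts gives Wilcoxon rejection in 9.2% or 16.7% of trials, and Welch rejection in 10.0% or 17.6%. With log-SD 0.5 the Wilcoxon figures are 5.5% and 6.9%. Changing the test does not remove this effect; a common price list does.

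**The case against.** Much of the case on the other side stands.

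- Mean (SD) will be reported, so a reader will see both mean costs. What is missing is inference on their difference.
- Use of Wilcoxon for cost is an inference from the catch-all wording. It is a reasonable one, since no other method for a continuous outcome is offered, but the plan does not say it outright.
- The high percentages need log-SD ratios of about 2.7 to 3.3. Mild differences give about 7%. The fixed drug cost matters much only if it is a large share of the cost being compared. That is possible for pharmacy cost and less likely for total admission cost. The documents give neither share.
- A reader might infer that costs are compared as incurred in different calendar periods. The documents do not say so. They say that costs will be calculated, by component, which is compatible with a single price list. The price year is unstated, and that is all that can be said.
- A reader might also infer that the plan could falsely confirm that QLB saves money. That is not shown. With QLB the less variable cohort, the error falls almost entirely on the side of QLB appearing costlier, and a rise in prices would push the same way. The direction would turn if QLB costs were the more variable, but the fixed drug component points the other way.
- Cost is not the primary outcome, it was not powered, and the comparison is historical and non-randomised. A better test leaves that confounding in place.

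None of this supplies an interval for the quantity that the hypothesis concerns.

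**Conclusion.** The point holds in a limited form. The plan states an expectation about overall pharmacy cost and provides no inference on the difference in mean cost. If the cost distributions differ in shape, the rank-sum test can signal a difference when the means are equal. The size runs from no inflation with equal shapes, through about 7% and 14%, to 35–67% in the extreme settings (26–59% with 27 QLB patients), against 2.5% expected. All of these rest on assumed lognormal costs, assumed spreads and an assumed split of 45 and 30. The extreme figures illustrate how far the effect can go and do not estimate what this study would see.

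Under these assumptions the likely harm is a real saving missed or reported as a loss. With QLB truly 10% cheaper on average and 45/30, the three extreme settings still declare it costlier in about 10%, 24% and 49% of trials, and cheaper in under 2%. A reversal at a 20% saving needs strong skew: 29% for log-SD 0.3 versus 1.0, but 0.6% for 0.3 versus 0.6.

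This is a worthwhile improvement to a secondary analysis and does not threaten the primary result.

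**What to change.** State in the analysis section that the main cost analysis is the QLB minus TEA difference in arithmetic mean pharmacy cost, and likewise in mean total admission cost, each with a bootstrap 95% confidence interval. Keep the Wilcoxon test as a supporting result. Name the price year and the source of unit costs, and value both cohorts' resource use with one price list. Label the cost comparison as exploratory, since common pricing does not remove other differences between the two periods.

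No further patients or outcome data are needed: the work is a short bootstrap routine and one price table. The intervals for mean cost will be wider than the rank test would suggest. With about 30 patients in a cohort and heavy skew, bootstrap coverage will fall somewhat below 95%, and the report should say so.

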Following the block, subjects will proceed to the operating room where they will undergo a standard general anesthetic with endotracheal intubation (desflurane or isoflurane in a mixture of air/oxygen). The dosing of intraoperative opioids will be left to the discretion of the attending anesthesiologist in the room.

In the Post-Anesthesia Care Unit (PACU) and on the postoperative floor, subjects will have access to oxycodone 5-15 mg PO q3h prn for rescue analgesia (the primary outcome measure). In the PACU, patients will also have access to intravenous hydromorphone if the oral opioid

provides inadequate relief. Finally, subjects may receive a standard multimodal analgesia regimen consisting of:

- Acetaminophen 975 mg PO q6h (beginning in preop holding)
- Gabapentin 600 mg PO once in holding, then 100 mg PO tid thereafter
- Ketorolac 15 mg IV prior to skin closure

While this standard regimen is expected, it may vary per clinical care team judgement and/or preference. Any alterations in this standard regimen will not be considered a protocol deviation.

Assessments

Patient assessments will be performed or recorded by a research assistant twice daily (unless otherwise specified). Assessments made after discharge will be recorded by subjects who will be provided with a diary to document the outcomes. Outcomes to be measured include:

Opioid consumption. Cumulative opioid consumption over 48 hours is the primary outcome measure. Data will be drawn from PACU records and from the nursing medication records on a twice-daily basis. Post discharge opioid use will be tracked in the take-home patient diary. The patient will be called at 7 days after surgery to collect.

NRS-11. The 11-point Numeric Rating Scale (0-10) will be used as a secondary outcome measure. Two measures will be taken with each assessment, one at rest and one with coughing. These will be conducted preoperatively, 30 minutes after arrival to PACU, and at time points 8 hrs., 24 hrs., 36 hrs. 48 hrs, 72 hrs, 96 hrs., 120 hrs., 144 hrs. and 168 hrs.

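### The eight shared adverse events are gathered by a research assistant in the QLB cohort but from routine charts to discharge in the TEA cohort, which likely biases the comparison against QLB

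*Combined protocol and SAP*

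**What the plan says.** Purpose of the Study makes the comparison a hypothesis: QLB is expected to bring "fewer complications such as block failure, urinary retention, and pruritis". Data Analysis & Statistical Considerations plans Wilcoxon and Fisher tests between cohorts for opioid use, pain and the other secondary outcomes, without adjustment.

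The list of opioid-related adverse events reads the same for both cohorts: "Incidence of nausea, vomiting, ileus, constipation, orthostasis, pruritis, urinary retention, respiratory depression". The way the events are collected differs.

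- **QLB (Assessments).** "Patient assessments will be performed or recorded by a research assistant twice daily (unless otherwise specified"). Also: "Assessments made after discharge will be recorded by subjects who will be provided with a diary to document the outcomes". The adverse-event item has no definition, method, schedule or end date of its own.
- **TEA (historical-data text just before Selection of Subjects).** The source is "data from the patient's electronic medical record if available", drawn from "hospital notes, anesthesia notes, medical history, medications, pain service notes, and flowsheets from admission to discharge". The stated aim is comparison with the prospective cohort.

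The plan gives no common event definition, source, window or sensitivity analysis for these eight events.

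**The concern.** Identical wording covers two different measurements. Itch, nausea and constipation are symptoms whose recorded frequency depends on whether someone asks. A research assistant visiting twice a day can be expected to find more of them than notes written for clinical care. A window without a stated end can only add QLB events, whereas the TEA record stops at discharge.

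If so, part of any difference in incidence reflects ascertainment rather than analgesic technique. A real advantage of QLB could be hidden, or a false excess with QLB could appear. Pruritus and urinary retention are at stake in particular, because the purpose statement names both.

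**Working it through.** **The plan's own figure.** The only calculated figure is the sample size for 48-hour opioid use. With a margin of 20% × 20 mg = 4 mg, SD 5.2 mg, power 0.8 and one-sided alpha 0.025 (equivalent to two-sided 0.05), n per group = 2 × 5.2² × (1.960 + 0.842)² / 4² = 26.5, so 27 per group and 54 in total. This reproduces, and the present point does not touch it. No calculation is given for adverse events.

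**Inputs.** From the documents: 30 historical patients; 27 per group required and 45 to be recruited, so QLB is run at 27 and at 45; Fisher exact tests. Assumed, because the documents give no rates: the true event rates, the share of events captured in each cohort, and a two-sided 0.05 level for the Fisher test.

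**Formulas.** Recorded rate = true rate × capture. The chance of a significant result in a given direction is the sum of Bin(x; n_QLB, recorded QLB rate) × Bin(y; 30, recorded TEA rate) over all pairs (x, y) with two-sided Fisher p ≤ 0.05 and the observed difference in that direction.

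**Case A: QLB truly better, 15% against 45%.** With 90% capture the recorded QLB rate is 0.15 × 0.9 = 13.5%.

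| Capture QLB / TEA | Recorded TEA rate | Recorded difference (QLB − TEA) | Chance of showing fewer with QLB, n=27 | n=45 |
|---|---|---|---|---|
| 100% / 100% | 45% | −30 points | 0.659 | 0.776 |
| 90% / 90% | 40.5% | −27 | 0.597 | 0.711 |
| 90% / 80% | 36% | −22.5 | 0.459 | 0.565 |
| 90% / 70% | 31.5% | −18 | 0.319 | 0.405 |
| 90% / 60% | 27% | −13.5 | 0.194 | 0.252 |
| 90% / 50% | 22.5% | −9 | 0.099 | 0.130 |

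The 90% / 90% row separates the two effects. Equal under-capture costs about 0.06 of power; the rest of the loss comes from the gap between cohorts.

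**Case B: no true difference, 30% in both.** With 90% capture the recorded QLB rate is 0.30 × 0.9 = 27%.

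| Capture QLB / TEA | Recorded TEA rate | Recorded difference (QLB − TEA) | Chance of a false finding that QLB is worse, n=27 | n=45 |
|---|---|---|---|---|
| 100% / 100% | 30% | 0 points | 0.017 | 0.018 |
| 90% / 80% | 24% | +3 | 0.032 | 0.036 |
| 90% / 70% | 21% | +6 | 0.057 | 0.066 |
| 90% / 60% | 18% | +9 | 0.098 | 0.116 |
| 90% / 50% | 15% | +12 | 0.162 | 0.193 |

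**Other assumptions.** With 30 per group, full QLB capture and true rates of 20% and 40%, the chance of showing fewer events with QLB falls from 0.298 (full TEA capture) to 0.119 at 80% and 0.029 at 60%. At 50% the recorded TEA rate is 0.40 × 0.5 = 20%, and the true 20-point benefit disappears from the data.

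These figures model unequal capture only. Extra QLB events from a longer window are not included and would move the result further in the same direction.

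**The case against.** The strongest reply is that the two methods may be closer than they look. Assistants may perform or merely record assessments, so QLB events may also be copied from the chart. The TEA sources include pain service notes, which the plan describes elsewhere as daily, and such notes could plausibly cover pruritus and retention. QLB assessors are not described as blinded, and under-recording by them would push the other way; if QLB capture fell below TEA capture, the bias would reverse. All of this stands. It makes the size uncertain, and for some events the direction. It does not align the methods, because nothing in the plan requires QLB events to come from the chart.

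Three stronger readings are tempting, and the documents do not support them.

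- **That QLB adverse events are certainly collected by diary up to day 7.** The diary sentence covers outcomes in general. The specific mention of the diary, and the sentence "The patient will be called at 7 days after surgery to collect", belong to the opioid-consumption item. Pain and sleep have schedules reaching about 168 hours; the adverse-event item has none.
- **That urinary retention is counted or costed twice in TEA.** It does appear both among the opioid-related events and among "adverse events related to the epidural including evidence of hypotension, urinary retention, inability to ambulate per physical therapy". But no complication total is defined, and the event-specific cost items cover only opioid-related events. Two listings are not two counts.
- **That the design certainly biases against QLB.** This is the expected direction, not an established one, for the reasons above.

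**Conclusion.** The point holds as a mismatch of source and window, with a likely bias against QLB in the eight shared events. Confidence is moderate. The size depends on rates that the documents do not give. Under the assumptions shown, a modest gap (90% against 80% capture) lowers the chance of showing a true 15% against 45% benefit from 0.66 to 0.46 with 27 QLB patients, and from 0.78 to 0.57 with 45. It leaves the false finding that QLB is worse at 0.03 to 0.04. A severe gap (90% against 50%) gives 0.10 and 0.13 for the true benefit, and 0.16 and 0.19 for the false finding, against about 0.02 with equal capture.

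The conclusion is limited to the shared events. Events listed for only one cohort, such as hypotension for TEA or hip flexor weakness for QLB, are a separate matter. This is a cheap improvement to a named secondary hypothesis.

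**What to change.** For every between-cohort adverse-event comparison:

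1. Abstract the eight shared events in both cohorts from the electronic record sources already listed for the historical group, with the same written event definitions and the same abstraction form.
2. Use one fixed window from PACU arrival that nearly all patients spend in hospital, for example the first 48 hours, matching the primary outcome. The documents give no length-of-stay figures, so check this choice against the data, and report how many in each cohort were discharged before the window ended. Do not simply stop at discharge: length of stay is itself a compared outcome, so that rule would give unequal time at risk.
3. Count urinary retention once per patient.
4. Report events found by the research assistant or in the diary as QLB-only descriptive data.

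The cost is a small amount of chart abstraction for the QLB patients and a wording change, with no new patients or visits. The downside is that mild, late or post-discharge events leave the comparison, although they remain in the QLB description.
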